2.2 Objectives

The objective of this study is to test the hypothesis that using nasal high flow oxygen (HFNO) improves ventilation during cardiac implantable electronic device procedures performed with conscious sedation.

2.3 Trial design

A randomized controlled design will be used with participants randomized in a 1:1 ratio to the following treatment conditions:

- Oxygen supplementation through a standard facemask; or
- Nasal high flow oxygen.

3 METHODS

3.1 Study setting

Peter Munk Cardiac Centre Cardiac Cath Labs at Toronto General Hospital, University Health Network.

3.2 Eligibility criteria

3.2.1 Inclusion criteria

1. Adults undergoing an elective cardiac implantable electronic device procedure in the Peter Munk Cardiac Centre Cardiac Cath Labs with conscious sedation administered by an Anesthesia Assistant (de novo and replacement/revision procedures). As per the hospital's policy for conscious sedation administered by Anesthesia Assistants (38.40.001), these patients will have been determined by the Anesthesiologist to be appropriate to receive care from the Anesthesia Assistants.

3.2.2 Exclusion criteria

1. Under 16 years of age (excluded from this study as they are considered pediatric patients).
2. Underlying condition requiring chronic oxygen supplementation.
3. Diagnosed respiratory condition with confirmed current hypercapnia. Hypercapnic COPD or obesity hypoventilation syndrome with PaCO₂ during current admission over 45mmHg.
4. Pre-existing untreated pneumothorax.
5. Transesophageal echocardiography planned for the procedure.
6. Active nasal bleeding.
7. Complete nasal obstruction.
8. Recent upper airway surgery or base of skull fracture.
9. Previous participation in the study.

3.3 Interventions

3.3.1 Intervention description

All randomized participants will receive usual care in regard to the medications used for sedation and physiological monitoring or other interventions to support respiratory function that are considered necessary to be initiated during the procedure by the clinicians. As per the hospital policy for conscious sedation administered by Anesthesia Assistants (38.40.001), oxygen therapy is administered as indicated and prescribed to maintain oxygen saturation greater than 93%. In this study, Anesthesia Assistants will follow this policy. Also in accordance with this hospital policy (38.40.001), the Anesthesia Assistants administer a combination of sedation to target the level of conscious

sedation, which is defined as “A drug-induced depression of consciousness during which patients respond purposefully to verbal commands, either alone or accompanied by light tactile stimulation.” As such, by practicing in accordance with this hospital policy, the level of sedation being administered by the Anesthesia Assistant for participants included in this trial is being ‘standardized’. The hospital policy does not stipulate any dose ranges of the different classes of sedative medications to be used and there will be no restrictions on the type or dose of sedation used by Anesthesia Assistants. The actual doses of sedation used will be recorded. Only the device used for oxygen supplementation delivery will differ between groups in the following ways:

Facemask oxygen supplementation

Supplemental oxygen through a facemask with the flow rate chosen by the clinician responsible for sedation as per their standard practice. The oxygen flow rate is typically commenced at 6 liters per minute and can be titrated up to 15 liters per minute.

High flow nasal oxygen

The Optiflow device (Fisher and Paykel Healthcare, Auckland, New Zealand), heated breathing tube and chamber, and nasal cannula will be used. This system is a humidifier with an integrated flow generator, able to humidify respiratory gases and deliver them down a heated breathing tube and through the nasal cannula interface. The gas temperature will commence at the ‘High’ setting (ranges 30-32° Celsius) and titrated downwards if the patient complains of irritation. The gas flow rate will commence at 30 liters per minute prior to sedation administration and be titrated up to 70 liters per minute as tolerated by the patient after sedation has been administered. The fraction of oxygen in the gas will be commenced at 50% (same as that delivered from 6 liters per minute via facemask) and can be titrated upward according to patient requirements (i.e. increased if there is evidence of hypoventilation, airway obstruction or inadequate oxygenation, decreased during use of diathermy). Anesthesia Assistants at the site will be provided with training in the use of this mode of oxygen delivery prior to study commencement.

3.3.2 Modifications

The researchers may remove a potential participant that has been enrolled in the study if:

- The health care team decides that the participant will not receive sedation during their procedure for an unforeseen reason. Under these circumstances, the participant will not be randomized in the study, and their data will not be included.

If a participant decides to leave the study, they will have the right to request withdrawal of information collected about them. The information that was collected before they left the study will still be used in order to help answer the research question.

3.3.3 Adherence

Due to the short duration of the trial and the nature of the intervention, strategies related to trial retention and adherence to follow-up will not be required.

All randomized participants will receive usual care in regard to the medications used for sedation and physiological monitoring or other interventions to support respiratory function that are considered necessary to be initiated during the procedure by the clinicians. As per the hospital policy for conscious sedation administered by Anesthesia Assistants (38.40.001), oxygen therapy is administered as indicated and prescribed to maintain oxygen saturation greater than 93%. In this study, Anesthesia Assistants will follow this policy. Supplemental oxygen through a facemask with the flow rate chosen by the clinician responsible for sedation as per their standard practice. The oxygen flow rate is typically commenced at 6 liters per minute and can be titrated up to 15 liters per minute. Percentage of hemoglobin saturated with oxygen (SpO₂) will be measured continuously throughout procedures as part of routine clinical practice through the anesthetic machine.

The use of high flow nasal oxygen will result in no difference in the time required for the intervention vs. routine standard of care. No additional visits will be required following completion of the elective cardiac implantable electronic device procedure.

3.3.4 Concomitant care

There are no restrictions on concomitant care for this trial.

It is possible that a deeper level of sedation is deemed to be required at some point during the procedure. This would occur only for unforeseen reasons, which can not be anticipated ahead of time. If 'deep' sedation is required for a portion of the procedure, the Anesthesiologist overseeing the Anesthesia Assistant would be required to be present. However, the allocated randomization for oxygen supplementation will not need to be changed. The Anesthesiologist will be able to increase the flow rate to increase oxygen supplementation in the 'standard' care group or increase the FiO₂ and flow rate in the HFNO group however they deem necessary. In these circumstances, the Anesthesia Assistant would still be involved in the procedure and document any changes in oxygen supplementation used by the Anesthesiologist on the data collection form.

The Research Assistant (RA) will determine if prospective participants are already enrolled in other research trials in the Clinical Research Record through Electronic Patient Record (EPR). If a prospective participant is already enrolled in another trial, the RA will assess whether that trial intervention will also be implemented during the procedure. If not, the prospective participant will still be eligible for the high-flow nasal oxygen trial due to the short duration that this intervention is being implemented and also because the follow-up duration will be completed soon after the end of the procedure.

3.4 Outcomes

The selection of outcomes was informed by recommendations from the Sedation Consortium on Endpoints and Procedures for Treatment, Education and Research (SCEPTER) to assess differences between groups regarding the safety and efficacy of sedation.

Primary outcome: Peak transcutaneous carbon dioxide (TcCO₂) concentration.

Continuous TcCO₂ measurements will be recorded using the Sentec Digital Monitoring with VSign 2 sensor. TcCO₂ monitoring provides continuous, accurate (mean bias -0.1 mmHg) and precise (95% limits of agreement within 6 mmHg) estimates of arterial CO₂ (PaCO₂) when the sensor is placed on the earlobe.¹⁴ TcCO₂ monitoring may provide even more precise estimates of changes in PaCO₂ (mean bias 0.03 mmHg, 95% limits of agreement -0.44 to 0.38 mmHg).¹⁵

We have undertaken a preliminary study to evaluate the feasibility of using TcCO₂ monitoring as an outcome measure during nurse-administered sedation in the cardiac catheterisation laboratory. Continuous TcCO₂ measurements were recorded from patients undergoing procedures with nurse-administered sedation using the Sentec Digital Monitoring with VSign 2 sensor, starting before sedation was induced (for measurement of baseline TcCO₂) and ceasing at the end of the procedure. Participating sites were the Wesley Hospital, Holy Spirit Northside Private Hospital, Princess Alexandra Hospital and John Flynn Private Hospital. The feasibility of TcCO₂ monitoring in this population was confirmed with continuous recordings achieved from all participants without missing data. Changes in TcCO₂ concentrations are presented in Table 1.

Table 1. Changes in TcCO₂ concentrations during sedation (n=123)

	Mean	SD
Baseline pre-sedation TcCO ₂	37.3	4.6
Post-sedation mean TcCO ₂	42.3	5.8
Peak TcCO ₂	46.8	6.9
Change from baseline to peak TcCO ₂	9.4	5.6

Secondary outcomes

1. Mean transcutaneous carbon dioxide concentration measured throughout the whole procedure using the VSign 2 sensor.
2. Trajectory of transcutaneous carbon dioxide concentration as a function of time throughout the whole procedure using the VSign 2 sensor.
3. Area under the curve of oxygen desaturation: This is a composite measure comprising the incidence, depth, and duration of oxygen desaturation events. It is calculated as the difference between the threshold (90%) and actual oxygen saturation (SpO₂) summed every second during which oxygen saturation was below threshold).
4. Adverse sedation events: Adverse effects of delivering gas at a high flow rate through the nasal passages will be assessed. These include nose bleeding arising from damage to the

mucosal surface and pressure injury to skin from the device. The RA will inspect intervention group participants' skin integrity around the nasal region at the end of procedures to assess for these potentially anticipated as well as unanticipated adverse effects.

5. Patient satisfaction with sedation: The Iowa Satisfaction with Anesthesia Scale (ISAS) will be used to measure patient satisfaction with the anesthetic used during the procedure performed.
6. Costs associated with oxygen delivery: The amount of consumable equipment required for oxygen delivery used during procedures and throughout the recovery period will be measured using a data collection form specifically designed for this study.
7. Patient comfort of oxygen delivery: Participants will be asked to rate at the end of procedures their perceived overall comfort with the oxygen delivery device used during the procedure using a 6-level ratings scale.
8. Anesthesia Assistant rating of difficulty maintaining oxygenation status.
9. Anesthesia Assistant rating of difficulty using oxygen delivery device.

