Outcome: Area under SpO₂ 90% desaturation curve

Timeframe: From the time between first sedative medication administration to the end of the procedure. Estimated duration of procedures is 30 minutes to 120 minutes.

Description: Difference between the threshold (90%) and actual oxygen saturation (SpO₂) summed every second during which oxygen saturation was below threshold.

Outcome: Adverse sedation events

Timeframe: From the time between first sedative medication

administration to the end of the procedure. Estimated duration of procedures is 30 minutes to 120 minutes.

Description: The Anaesthesia Assistant will be asked to complete the Tracking and reporting outcomes of procedural sedation (TROOPS) tool at the end of procedures. Completion of the tool requires identification and description of the adverse event, the intervention, the outcome and the overall severity of the adverse event.

Outcome: Patient satisfaction with sedation

Timeframe: After the participant has reached phase 2 post-anesthetic recovery. Estimated to be 30 minutes after procedure has finished.

Description: Iowa Satisfaction with Anesthesia Scale

Outcome: Costs associated with oxygen delivery

Timeframe: From the time between first sedative medication administration to the end of the procedure. Estimated duration of procedures is 30 minutes to 120 minutes.

Description: Anesthesia Assistants will document devices used for supplemental oxygen delivery and airway management

in both groups as per their usual practice in the anesthesia monitoring system.

Outcome: Anesthesia Assistant rating of difficulty maintaining oxygenation status

Timeframe: To be completed as soon as possible after the end of the procedure (within about 5 minutes).

Description: 6-level rating scale from “extremely difficult” to “extremely easy”

Outcome: Anesthesia Assistant rating of difficulty using oxygen delivery device

Timeframe: To be completed as soon as possible after the end of the procedure (within about 5 minutes)

Description: 6-level rating scale from “extremely difficult” to “extremely easy”

Outcome: Patient comfort of oxygen delivery

Timeframe: After the participant has reached phase 2 post-anesthetic recovery. Estimated to be 30 minutes after procedure has finished.

Description: 6-level rating scale from “maximal discomfort” to “maximal comfort”

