3.5 Participant timeline

Data for this study will be collected by the RA and entered into an electronic data platform supported by REDCap™ (Research Electronic Data Capture Vanderbilt University, Nashville, TN, USA) at three time points: (T1) at baseline (prior to procedures); (T2) during the procedure; and (T3) on hospital discharge.

After receiving participant consent, demographic information and eligibility to participate will be confirmed at T1. Transcutaneous carbon dioxide (TcCO₂) monitoring and pulse oximetry will be measured continuously at T2. Adverse sedation events, patient comfort with sedation, difficulty maintaining oxygen saturation and using the device, and cost associated with the oxygen delivery device will be assessed at T3. Patient satisfaction with sedation will also be assessed at this time using the Iowa Satisfaction with Anesthesia Scale (ISAS) through REDCap™.

	During Pre-procedure procedure	Post- procedure
--	---	----------------------------

TIMEPOINT	T1	T2	T3
ENROLLMENT:	X		
Eligibility screen	X		
Informed consent	X		
Allocation	X		
INTERVENTIONS:			
Facemask oxygen supplementation		X	
High flow nasal oxygen		X	
ASSESSMENTS:			
Demographic information and medical history	X		
Peak TcCO ₂ concentration		X	
Mean TcCO ₂		X	
Area under the curve of oxygen desaturation		X	
Adverse sedation events			X
Patient satisfaction with sedation			X
Costs associated with oxygen delivery			X
Anesthesia Assistant rating of difficulty maintaining the patient's oxygenation			X

status

Anesthesia Assistant rating of difficulty using oxygen delivery device	X
Patient comfort of oxygen delivery	X

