3.10 Data collection

3.10.1 Trial procedures and evaluations

Instruments used to measure outcomes

Transcutaneous carbon dioxide concentrations: PI [name] will provide training to the RA in use of the transcutaneous carbon dioxide monitoring device and other data collection procedures. The RA will attach the Sentec VSign 2 sensor to the participant's forehead using a multi-site attachment ring. Once the Sentec Digital Monitoring System displays a stabilized TcCO₂ level, the monitor will be covered with a drape so that it is not visible to research staff or clinicians during the procedure. The monitor will not be used by the clinicians to guide treatment. Data will be downloaded to a computer using the USB port on the monitor. TcCO₂ monitoring provides continuous, accurate (mean bias within 2 mmHg) and precise (95% limits of agreement within 6 mmHg) estimates of arterial CO₂ (PaCO₂) in sedated patients.¹⁴

Pulse oximetry: Percentage of hemoglobin saturated with oxygen (SpO₂) will be measured continuously throughout procedures as part of routine clinical practice through the anaesthetic machine. We will access the DREAM (Drug Reconciliation and Electronic Anesthesia Monitoring) system to download this data. Unreliable SpO₂ measurements will be filtered out if a pulse rate is not detectable.

Tracking and reporting outcomes of procedural sedation tool.²³ This tool was developed, using a consensus process, by members of a multidisciplinary society who had demonstrated capacity, dedication and competence in research and/or clinical experience in procedural sedation. Completion of the tool requires identification and description

of the adverse event, the intervention, the outcome and the overall severity of the adverse event. The Anaesthesia Assistant will be asked to complete this tool at the end of procedures. It takes approximately 2 minutes to complete.

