3.12 Statistical methods

3.12.1 Outcomes

For the primary outcome, peak TcCO₂ will be compared between the intervention and control groups using a Bayesian hierarchical model with baseline TcCO₂ concentration included in the model as a covariate as is recommended for this type of design.²⁶ Bayesian models will also be used to compare secondary outcomes among the randomization groups. Prior distributions for all model parameters will initially be chosen to be non-informative and will be adjusted as necessary to improve model fit. The posterior distributions of parameters and quantities of interest will be presented as well as their medians and 95% highest-density intervals (HDI). Subgroup analyses will be conducted to compare the effects of HFNO with standard care in patients who have a diagnosis of sleep apnea and those who have a cardiac resynchronization therapy device implant (the variables used for stratification) by including these variables in the model as interaction terms.

In addition to comparing the peak TcCO₂, per-second TcCO₂ levels will be compared between randomization groups using methods of functional data analysis. Functional observations will be estimated by fitting a B-spline basis to the TcCO₂ data, subject to a roughness penalty on the second derivative of the estimated function. Common features of these estimated functions will be examined using functional principal component analysis (FPCA). A formal comparison of TcCO₂ levels between randomization groups will be performed using functional analysis of variance (FANOVA). Results of this functional analysis will be compared to those obtained in the bayesian analysis on just the peak TcCO₂ levels.

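### Outcome 4 (adverse sedation events) has two definitions, and skin injury is actively sought only in the HFNO arm; if those findings are compared between arms and facemasks injure any skin, the comparison is biased against HFNO

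*Combined protocol and SAP*

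**What the plan says.** Three places in the combined protocol and SAP give this outcome its content.

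- **Section 1, trial summary.** Adverse sedation events are what the TROOPS form records: "The Anaesthesia Assistant will be asked to complete the Tracking and reporting outcomes of procedural sedation (TROOPS) tool at the end of procedures". Nothing limits this to one arm.
- **Section 3.4, outcome 4.** The name is the same but the content differs: "Adverse sedation events: Adverse effects of delivering gas at a high flow rate through the nasal passages will be assessed". The events named are nose bleeding and pressure damage to the skin. TROOPS is not mentioned. The stated assessment is "The RA will inspect intervention group participants", meaning a look at the skin around the nose when the procedure ends, for expected and unexpected effects alike.
- **Section 3.10.1.** TROOPS ("The Anaesthesia Assistant will be asked to complete this tool at the end of procedures") and adverse effects appear as two separate items. The second repeats the inspection of the intervention group only.

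Two general sentences bear on comparison. Section 3.4 says the choice of outcomes followed recommendations meant "to assess differences between groups regarding the safety and efficacy of sedation". Section 3.12.1 says "Bayesian models will also be used to compare secondary outcomes among the randomization groups". Neither says whether the inspection findings are included. Section 3.14 requires reporting of any adverse event in either arm, but it is not an active check.

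**The concern.** There are two linked problems. First, whoever programs the analysis cannot tell whether outcome 4 is the TROOPS record, the inspection findings, or both. That holds without any assumption about injury rates.

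Second, under the section 3.4 content, skin injury is actively looked for in one arm only. No section gives facemask participants an inspection. Their injuries can reach the data through TROOPS or general adverse event reporting, and the documents do not say that either prompts for skin injury. Section 3.9.1 confirms that personnel know the allocation.

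Section 2.1 says the possible disadvantages of HFNO should be evaluated, and this is the outcome that records device harm. If the findings are compared, an excess under HFNO could reflect harm or closer looking. The two could not be separated later, because control inspections that were never made cannot be recovered.

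**Working it through.** The plan states no adverse event rate and no power for this outcome, so there is no figure of its own to reproduce. Its one power calculation (130 participants, peak TcCO₂) plays no part here.

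**Step 1. Direction and size of the bias.** Let p_H and p_C be the true injury rates under HFNO and facemask, and s_H and s_C the shares detected.

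- Observed difference: s_H × p_H − s_C × p_C.
- Difference with equal detection at s_H: s_H × (p_H − p_C).
- Bias: (s_H − s_C) × p_C.

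The bias is positive, that is against HFNO, only if p_C > 0 and the facemask arm is checked less closely. With s_H = 1, p_C = q and s_C = s it is q × (1 − s).

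**Step 2. What it could amount to.** Everything below is illustrative. Assumptions: 75 per arm (150 ÷ 2, from sections 2.3 and 3.6), the same true rate p in both arms, full detection under HFNO, independent Beta(1,1) priors, and a false signal defined as a 95% HDI for the risk difference lying wholly above 0. The plan sets no such threshold; it only says that posteriors, medians and 95% HDIs will be presented.

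Device injury analysed alone:

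| | p = 2% | p = 5% | p = 10% |
|---|---|---|---|
| Spurious difference, s = 0 (points) | 2 | 5 | 10 |
| Spurious difference, s = 0.5 (points) | 1 | 2.5 | 5 |
| Chance of false signal, s = 0 | 1.7% | 32.1% | 88.1% |
| Chance of false signal, s = 0.5 | 0.85% | 7.5% | 17.3% |
| Chance of false signal, equal detection | 0.4% | 1.6% | 2.1% |

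The s = 0 row is easy to check. No facemask injury is ever recorded, the smallest HFNO count that puts the HDI above 0 is 5 against 0, and the chance is P(Bin(75, p) ≥ 5). As a cross-check, a two-sided Fisher test at 0.05 gives 0.4%, 17.2% and 77.3% at s = 0.

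Pooled with other adverse events at an assumed background rate b = 10% in both arms, the spurious difference is (1 − b) × p × (1 − s). At s = 0 that is 1.8, 4.5 and 9.0 points, with false-signal chances of 4.8%, 12.2% and 33.7%. At s = 0.5 the chances are 3.3%, 5.6% and 10.5%, against about 2.3% with equal detection.

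**Step 3. When it vanishes.** If p_C = 0 the bias is 0 at any detection rate. If s_H = s_C it is 0 at any injury rate. If outcome 4 is TROOPS alone, or the inspection findings are only described for HFNO, they never enter the difference.

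**The case against.** The strongest reply is that section 3.4 describes monitoring of a new device. Its lead words concern high-flow gas through the nose, which a facemask participant does not receive, and the inspection is confined to the nasal region. Section 3.10.1 supports this: the costs item says explicitly that both groups are covered and compared, while the adverse effects item names the intervention group and mentions no comparison. This reading is at least as natural as the comparative one. But the plan does not state it, and section 3.12.1 makes no exception for these findings.

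It is also fair that TROOPS is open to both arms, so under the trial summary's definition there is no bias from the inspection. And the injury and detection rates above are assumed. The 88.1% needs a 10% injury rate, a stand-alone endpoint and no facemask injury found by any route; the last sits badly with two reporting routes open to both arms.

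A reader might also infer that the assessment times conflict, since section 3.5 defines T3 as hospital discharge. The documents do not support making much of this. In the trial summary, the window in which events count and the time the form is completed agree. T3 also holds ratings that the trial summary wants within about 5 minutes and patient reports at about 30 minutes, so discharge is a loose label for everything at T3.

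Finally, a shared checklist used by an unblinded research assistant does not guarantee equal detection. That stands.

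**Conclusion.** The double definition is established by the text. The bias is conditional: it arises only if the inspection findings enter the between-arm comparison and facemasks cause some skin injury that is detected less often. Its direction is then against HFNO. Its size cannot be given, because the documents contain no injury rate and no detection rate. Under the stated assumptions the effect is small at a true rate of 2% and can matter from about 5%; nothing in the documents shows which rate applies.

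A reader might infer that the safety comparison is biased as planned, or that a false harm signal is likely. The documents support neither, because they do not say that the inspection findings will be compared. The point touches one component of one of nine secondary outcomes and leaves the primary outcome and sample size untouched. It should still be corrected, because the change is cheap before data collection and cannot be made afterwards.

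**What to change.** 1. Define outcome 4 once, as TROOPS in both arms, in section 1 and section 3.4. List device injury as a separate item.
2. Change sections 3.4 and 3.10.1 to read, for example: *The RA inspects the skin at device contact points and records nose bleeding in participants of both groups, at the same time and with the same checklist.*
3. If inspection stays HFNO-only, state instead: *Inspection findings are descriptive for the HFNO group and are excluded from the between-arm comparison in section 3.12.1.*

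Option 2 costs about 75 minutes of existing research assistant time (75 controls × an assumed 1 minute each) and a line on the form. It improves the balance of detection without guaranteeing it, since the assistant is unblinded. Option 3 costs one sentence, but gives no comparison of device injury.
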